## PROTOCOL SUMMARY

Aortic stenosis (AS) is the most common primary valve disease leading to surgery or catheter intervention in Europe, with a growing prevalence due to the aging population. Severe AS is associated with significant morbidity and mortality and is treated by surgical valve replacement (SAVR) or transcatheter aortic valve implantation (TAVI). However, significant coronary artery disease (CAD) is reported in more than 60% of patients with AS, and this concomitant CAD needs to be correctly assessed because untreated significant CAD is associated with adverse outcomes. Current guidelines recommend intra-coronary pressure measurement using either fractional flow reserve (FFR) or non-hyperemic pressure ratios (NHPR) for the assessment of intermediate coronary artery lesions before revascularization. However, correctly identifying hemodynamically significant coronary stenoses by FFR or NHPR is difficult in patients with AS because of the hypertrophic remodeling related to the valve pathology, which interferes with coronary blood flow in the microcirculation and reduces the accuracy of FFR and NHPR. This has resulted in substantial controversy in this field of coronary artery disease and there is currently no clear guideline for the management of AS patients with concomitant CAD. Recent technological advances now permit the concomitant evaluation of FFR/NHPR and microcirculatory function at the time of cardiac catheterization. Using this technology, we will simultaneously evaluate the hemodynamic significance of coronary stenoses (using FFR and a NHPR - Resting Full cycle Ratio [RFR]) and the microcirculatory function (Index of Microcirculatory Resistance, IMR) in patients with AS and CAD prior to SAVR/TAVI. One hundred patients with AS and intermediate CAD will be included in the study. Of them Eighty will undergo AVR and at least 58 will undergo the follow-up at 6 Months. During routine pre-valve replacement cardiac catheterization, measurement of intermediate CAD lesions (by FFR and RFR) and IMR will be performed in duplicate using new software. These measures of CAD severity will be compared with a gold standard non-invasive test (single photon emission computed tomography [SPECT]). This will validate the use of RFR and determine if IMR can be used to improve the ischemia prediction of FFR. In addition, the patients undergoing TAVI the LVEDP will be measured immediately before and after valve implantation and FFR, RFR and IMR will be measured after valve implantation. Subsequently, when these patients undergo a post-intervention (whether SAVR or TAVI) evaluation 6 months after valve replacement, the effect of valve replacement on FFR, RFR and IMR (again in duplicate) will be determined. This will be the first study measuring these parameters before and 6 months after valve replacement. The data will be used to calculate a 'corrected' FFR (or RFR) based on microcirculatory function in these patients, which can then be used in the future to correctly evaluate CAD pre-intervention in patients with AS. This will translate into more efficient management of patients with AS. Fewer of these patients will unnecessarily undergo coronary artery bypass grafting or stenting when the CAD does not need to be treated and, conversely, in those who do require treatment of the CAD, revascularization can be carried out during a single surgery/intervention, avoiding multiple high risk procedures in patients who are already at high peri-operative/peri-interventional risk.

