If TAVI/SAVR results in a significant improvement in LV remodelling and microvascular function, it should be expected that the current invasive gold-standard for measuring microvascular resistance (IMR; index of microcirculatory resistance) would improve several months after the valve intervention. If this is the case then the FFR measurement should be more accurate (as it is in patients without aortic stenosis). The question is whether a pre-TAVI/SAVR index (based on a combination of FFR and IMR) could be used in the future for assessing intermediate lesions in these patients. Developing a “corrected” FFR measurement of intermediate coronary artery lesions based on the presence or absence of microvascular dysfunction would be very useful in the pre-operative work-up of patients with aortic stenosis and would have important prognostic implications. This will be accomplished by first determining the FFR 6 months after intervention (TAVI or SAVR), when it is anticipated that the microvascular function would have returned to normal, and comparing this with the FFR prior to the intervention to determine if there is a significant change in the FFR after intervention. At the same time microvascular function will be assessed in order to develop a “corrected” FFR, which can be used in the future to determine whether or not coronary lesions need to be revascularized in patients with aortic stenosis.

The theoretical model of a serial stenosis by the AS and the coronary narrowing in our study is explained in the figure 1 in the publication of Zelis et al. It is expected that the FFR will indeed decrease after TAVI and that there will be an acute (change of intercept) and chronic (change of slope) effect of the procedure on the coronary resistance. To separate these two issues we will try to measure the FFR immediately after TAVI and 6 months after TAVI. In addition the left ventricular filling pressure/ end-diastolic pressure (LVEDP) will be measured during the TAVI procedure immediately before and after valve implantation. The measurement (the delta LVEDP) will be an important marker of the “intercept” that changes acutely. To make sure the measurements of IMR, FFR and RFR are correct these will be performed twice and an average value will be used. This will also allow us to test the reproducibility.

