## 7. WITHDRAWAL FROM STUDY/STUDY DISCONTINUATION

A patient's participation in the trial is voluntary and the patient may refuse to participate or withdraw from the trial, at any time, without penalty or loss of benefits to which the patient is otherwise entitled.

Drop outs are defined as patients:

- who decided not to continue the study/not to perform the follow-up visits for whatever reason
- who died

When a participant is withdrawn from the study, follow-up by phone call will be continued, unless the patient does not provide consent to follow-up. However, all data collected prior to discontinuation from the study will be retained in the database.

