## 9. STATISTICS AND ANALYSIS

### 9.1 Sample Size

The sample size for the ***primary objective*** (change in FFR after aortic valve intervention) is based on previous measurements of FFR in patients with aortic stenosis, where a standard deviation of the data was reported. An expected mean FFR of 0.82 with a standard deviation of 0.08 was used in the calculation. Fifty eight (58) patients with pre- and post-interventions catheterizations will be sufficient to detect a reduction in the FFR from 0.82 to 0.79 with an alpha level of 0.05 and power of 0.80. A total sample of 100 patients with baseline measurements of which 80 patients will undergo (T)AVR without revascularisation (20% will undergo revascularisation) and in this way are eligible for pre-and post-intervention catheterization will allow for a 25 % drop-out during the follow-up phase of the study. Missing values will predominantly be at random. Therefore, the primary endpoint will be assessed using complete case analysis. To account for missing values, the number of patients will be increased from 58 to 80 (since missing data will be excluded from analysis).

For the ***secondary objective*** (comparison of FFR versus RFR): approximately 10-20% will have left main CAD, triple vessel disease, prior myocardial infarction or tandem lesions and will not be eligible for SPECT. One Hundred patients with baseline measurements will allow a 20% drop-out to end up with 80 patients with both baseline SPECT and invasive measurements. Yamanaka *et al.* found that a sample of 80 patients was necessary to determine the optimal cutoff value of iFR for indicating myocardial ischemia. Since RFR and iFR have an extremely high correlation (0.99), the same number of patients (80) is expected to achieve an area under the ROC curve of 0.70 with 0.90% power at a significance level of 0.05 in a 2-sided test.

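### Missing at random does not justify an unadjusted complete-case paired test of the change in FFR, and enlarging the sample from 58 to 80 does not remove the bias that selective loss can cause

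*Combined protocol and SAP*

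**What the plan says.** Section 9.1 (Sample Size) makes an assumption and draws the analysis from it: "Missing values will predominantly be at random. Therefore, the primary endpoint will be assessed using complete case analysis". Its remedy for missing values is numerical: "the number of patients will be increased from 58 to 80 (since missing data will be excluded from analysis". The same section says that the planned numbers "will allow for a 25 % drop-out during the follow-up phase of the study", and the Protocol Summary says "Of them Eighty will undergo AVR and at least 58 will undergo the follow-up at 6 Months".

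Section 9.2 compares FFR before and 6 months after intervention with a paired t-test or a Wilcoxon signed-rank test, without covariates.

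Section 7 defines drop-outs as patients who stop or do not attend follow-up, whatever the reason, and patients who died. On their earlier measurements it says: "However, all data collected prior to discontinuation from the study will be retained in the database".

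The documents contain no sensitivity analysis for missing FFR, no imputation or model-based alternative, no comparison of patients with and without a 6-month value, and no rule for deaths.

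**The concern.** The mean change among completers estimates the mean change in all eligible patients only if loss is unrelated to the change. Missing at random is a weaker condition: it lets loss depend on anything observed, including baseline FFR. Change from baseline is itself related to baseline. With equal SDs at the two visits and a correlation r below 1, patients with low baseline values tend to rise relative to the average, and those with high values tend to fall. Loss that depends on baseline FFR therefore shifts the completers' mean change, although it is missing at random in the technical sense. A larger sample estimates the shifted value more precisely.

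The follow-up visit is a repeat invasive catheterization after valve replacement, so death or refusal could plausibly be related to coronary severity or early course. The documents give no reason to assume otherwise.

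The Study Objectives read a null result as support for the validity of FFR/RFR in severe aortic stenosis, and a significant fall as evidence against it. The planned effect is only 0.03. A shift toward zero favours the first conclusion and a shift away from zero favours the second.

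**Working it through.** **Inputs from the documents.** Section 9.1 gives mean FFR 0.82 falling to 0.79 (change -0.03), SD 0.08, alpha 0.05, power 0.80, 58 pairs, 80 eligible patients and 25% drop-out. Section 9.2 gives the unadjusted paired test.

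**Assumptions, because the documents do not give them.** SD 0.08 at both visits; baseline/6-month correlation r from 0.3 to 0.9; odds ratio (OR) for loss from 1.25 to 3 per SD lower baseline FFR; a logistic model for loss.

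**Step 1. Reproduce the plan's figure.** A paired t-test with two-sided alpha 0.05, difference 0.03 and SD of the difference 0.08 needs n = 58 (power 0.802). The SD of the difference is 0.08 × √(2(1 − r)), so taking it as 0.08 implies r = 0.5.

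**Step 2. Size of the loss.** 25% of 80 is 20 losses and 60 completers (power 0.815). 80 − 58 = 22 losses, and 22/80 = 27.5%. Neither figure is a ceiling. They are two versions of the allowance and should be reconciled.

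**Step 3. General size of the bias.** Bias = missing share × (mean change in completers − mean change in drop-outs). At 22/80, each 0.01 difference in mean change gives 0.275 × 0.01 = 0.00275. At 20/80 it gives 0.0025. Offsetting the whole 0.03 would need a difference of 0.03/0.275 = 0.109.

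**Step 4. Loss that depends on baseline FFR (missing at random).** Let s be the amount, in SD units, by which the completers' mean baseline exceeds that of all eligible patients. Then

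complete-case change = −0.03 − (1 − r) × 0.08 × s.

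At 27.5% loss and OR 2, s = 0.175. With r = 0.5 this gives −0.03 − 0.5 × 0.08 × 0.175 = −0.037. The complete-case change at 27.5% loss is:

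| OR per SD lower baseline | r = 0.3 | r = 0.5 | r = 0.7 | r = 0.9 |
|---|---|---|---|---|
| 1.25 | -0.033 | -0.032 | -0.031 | -0.030 |
| 1.5 | -0.036 | -0.034 | -0.033 | -0.031 |
| 2 | -0.040 | -0.037 | -0.034 | -0.031 |
| 3 | -0.044 | -0.040 | -0.036 | -0.032 |

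At 25% loss the range is -0.030 to -0.043. In simulation of OR 1.5, 2 and 3 at each of these four correlations, regressing 6-month FFR on baseline FFR in completers and averaging over all eligible patients returned -0.030 every time.

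**Step 5. Loss that depends on a larger acute fall at TAVI.** This moves the estimate the other way. Assume a post-TAVI mean of 0.80, OR 2 per SD larger fall, 27.5% loss, and correlations (baseline–6 months, baseline–post-TAVI, post-TAVI–6 months) of 0.5, 0.6, 0.7 or of 0.7, 0.8, 0.8. If every patient had TAVI, the complete-case change would be -0.021 or -0.023. If 60% had TAVI (assumed; the documents give no split) and the mechanism acted only in them, it would be -0.024 or -0.026. With 58 pairs and SD of the difference 0.08, power falls from 0.80 to 0.61 at -0.024.

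**The case against.** Five points can be made for the plan.

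- **The phrase may be loose.** At random may simply mean unrelated to outcome, that is, missing completely at random. Complete cases would then be valid. This is a fair reading, but the assumption would still be stated without reasons or any check.
- **The bias may be small.** The same lesion is measured at both visits and duplicates are averaged, so r could be high. At r = 0.9 and OR 2 the bias is about 0.0014, roughly 5% of the effect. Even the 0.007 at r = 0.5 and OR 2 is below one standard error with 58 pairs (0.08/√58 = 0.0105). This stands as a limit on size, but it does not repair the inference.
- **The direction is unknown.** No section links refusal or death to FFR. Patients chosen for revascularisation have already left the 80, which may thin out low baseline values. Section 3.8 says that residual coronary disease should be reassessed, so more severe patients might attend more often. This stands too.
- **The post-TAVI measurement cannot carry the repair.** A reader might infer that every plausible mechanism is missing at random given data the trial collects. The documents do not support that. Section 3.8 and the Schedule of Events provide this FFR in TAVI patients only, and the Background says "To separate these two issues we will try to measure the FFR immediately after TAVI and 6 months after TAVI". Where the value is absent, loss driven by it is not missing at random.
- **Deaths differ from refusals.** A patient who died has no 6-month FFR, so patients alive at 6 months are a defensible target population. The plan would have to say so, and it does not.

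**Conclusion.** The concern holds as a fault of logic with a possible, unquantified effect. Missing at random does not license the unadjusted complete-case paired test, and increasing recruitment does not answer bias. Under baseline-dependent loss of 25 to 27.5% and a true change of -0.03, the complete-case change runs from about -0.030 to -0.044. Loss driven by a larger acute fall at TAVI would pull it toward zero, but only through TAVI patients. All of this rests on the assumed correlations, odds ratios and equal SDs.

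Two stronger readings go beyond the documents. One is that the primary result will be biased by a known amount or in a known direction; the inputs for that are not given. The other is that 22 of 80 is the most that can be lost. It is the allowance that leaves 58 pairs, and the stated 25% is 20 of 80.

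The change should be made. Confidence is high on the logic and low on the size.

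**What to change.** 1. Delete the word that derives complete-case analysis from missingness at random. State instead which variables the assumption conditions on.
2. For the primary estimate, use a two-timepoint likelihood-based mixed model or a baseline-conditional model. Include all patients who have valve intervention without revascularisation and a baseline FFR. Put valve procedure type in the model.
3. Keep the complete-case paired t-test as a sensitivity analysis.
4. Use post-TAVI FFR only as an auxiliary variable, in TAVI patients in whom it was measured.
5. State the target population with respect to deaths, for example by reporting the estimate among patients alive at 6 months.
6. Tabulate baseline FFR and IMR for patients with and without a 6-month FFR, with deaths separate from refusals.
7. Reconcile the 25% allowance (20 of 80) with the step from 58 to 80 (22 of 80).

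The cost is SAP wording and a standard model on data already collected. The analysis becomes slightly more complex, and it still relies on missing at random given the modelled variables.

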AS and intermediate CAD. They determined that the optimal iFR threshold for detecting ischemia compared with  $^{99m}\text{Tc}$  single-photon emission computed tomographic (SPECT) myocardial perfusion imaging was 0.82, while the cut-off for FFR was 0.83. This is in contrast to the large, outcome-based randomized controlled studies in patients without AS, and different to the current guideline cut-offs of  $\leq 0.89$  for resting indices and  $\leq 0.80$  for FFR. The RFR threshold for detecting ischemia has not yet been determined in patients with AS.

A more comprehensive study with performance of intra-coronary measurements before and after TAVI may help determine the effect of adverse LV remodelling and microvascular dysfunction on the hemodynamic measurement of coronary artery lesions in patients with severe AS. However, the timing of the follow-up measurements has not been clearly defined. Several studies have performed acute measurements pre- and post-TAVI but no invasive study (measuring FFR and/or resting indices) has been performed after allowing adequate time for reverse remodelling in order to really determine the effect of microvascular reverse remodelling on intra-coronary hemodynamic measurements. Exactly how long is needed after TAVI to ensure adequate myocardial and microvascular remodelling has occurred in order to appropriately use intra-coronary hemodynamic measurements is not known at this stage. One MRI-based study demonstrated a significant reduction in indexed LV mass from  $76\text{g}/\text{m}^2$  to  $68\text{g}/\text{m}^2$  within a few days. In another study, echocardiographic ejection fraction and LV global longitudinal strain improved significantly when measured 10 days after TAVI. However, indexed LV mass improvement was only significant during long-term (months-to-years) follow up. In a more recent, echocardiographic-based study, indexed LV mass decreased from  $117\text{ g}/\text{m}^2$  to  $100\text{ g}/\text{m}^2$  in a surgical aortic valve replacement (SAVR) group and  $114\text{ g}/\text{m}^2$  to  $108\text{ g}/\text{m}^2$  in a TAVI group after 3 months with further reductions at one year. Whether these global changes in LV remodelling translate into improvements in microvascular function, and hence improve the diagnostic accuracy of FFR is not yet known.

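### The 80 SPECT patients are presented as enough to determine a cut-off, but the calculation only powers a test of an AUC of 0.70 and gives no assurance about cut-off precision

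*Combined protocol and SAP*

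**What the plan says.** Section 9.1 sizes the SPECT comparison at 80 patients: 100 patients with baseline measurements "will allow a 20% drop-out to end up with 80 patients with both baseline SPECT and invasive measurements". The reason for 80 is that the earlier iFR study "found that a sample of 80 patients was necessary to determine the optimal cutoff value of iFR for indicating myocardial ischemia". Because RFR and iFR correlate at 0.99, the section then says that "the same number of patients (80) is expected to achieve an area under the ROC curve of 0.70", with a power, a significance level and a two-sided test attached.

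The cut-off is a live question in the protocol. The Background reports that the best iFR threshold in aortic stenosis against SPECT "myocardial perfusion imaging was 0.82, while the cut-off for FFR was 0.83", and contrasts these with guideline values of 0.89 for resting indices and 0.80 for FFR. It adds: "The RFR threshold for detecting ischemia has not yet been determined in patients with AS". Item 5 of the secondary outcomes under Study Objectives compares FFR and RFR against SPECT and against the earlier study. Under Expected Outcomes, the results are to be read as supporting that study or conflicting with it.

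For RFR against SPECT, section 9.2 plans ROC curve analysis. It gives no rule for choosing a cut-off, no confidence interval and no precision target.

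**The concern.** Showing that an index predicts ischaemia better than chance is one task. Locating the threshold at which it best does so is another, and it usually needs more information. Section 9.1 names the second task as the reason for 80 patients and then quotes an operating characteristic for the first. The iFR–RFR correlation carries the number from one index to the other; it adds no precision.

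What is at stake is how the result will be read. A single estimated RFR cut-off, reported without an interval, will be set beside 0.82 and 0.89 and described as agreeing or conflicting with the earlier study. The plan has nothing that tells a reader whether such a difference is larger than sampling error.

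**Working it through.** **Inputs from the documents.** N = 80; AUC 0.70; two-sided 0.05; power printed as 0.90%, read here as 90% (section 9.1). Thresholds 0.82 and 0.89 (Background), a gap of 0.07. Standard deviation 0.08, given for FFR only (section 9.1).

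**Assumptions.** Null AUC 0.50; ischaemia prevalence 20–50%; RFR standard deviation 0.05–0.12. The documents give none of these.

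**Step 1: reproduce the plan's figure.** Hanley–McNeil variance with n1 ischaemic and n0 non-ischaemic patients:

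V(A) = [A(1−A) + (n1−1)(a−A²) + (n0−1)(b−A²)] / (n1·n0), where a = A/(2−A) and b = 2A²/(1+A).

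- At A = 0.70: a−A² = 0.0485, b−A² = 0.0865. With 40/40, V = (0.21 + 39×0.0485 + 39×0.0865)/1600 = 0.00342, SE = 0.05848.
- At A = 0.50: both terms are 0.0833. V = (0.25 + 78×0.0833)/1600 = 0.00422, SE = 0.06495.
- Power = Φ[(0.20 − 1.96×0.06495)/0.05848] = Φ(1.243) = 0.893.

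So 80 reproduces (82 would give 90%), but only near balanced prevalence:

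| Ischaemic | n1/n0 | SE at 0.50 | SE at 0.70 | Power, N = 80 | N for 90% |
|---|---|---|---|---|---|
| 50% | 40/40 | 0.0650 | 0.0585 | 0.893 | 82 |
| 40% | 32/48 | 0.0663 | 0.0613 | 0.873 | 87 |
| 30% | 24/56 | 0.0709 | 0.0673 | 0.818 | 102 |
| 20% | 16/64 | 0.0812 | 0.0790 | 0.698 | 135 |

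No cut-off appears anywhere in this calculation.

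**Step 2: precision of a cut-off with 80 patients.** Simulation: RFR normal with equal variance in both groups; group separation d = √2·Φ⁻¹(AUC), which is 0.742 at AUC 0.70; within-group SD = overall SD/√(1 + π(1−π)d²), with π the prevalence; values rounded to 0.01; true optimum 0.82; cut-off chosen to maximise sensitivity + specificity − 1 (Youden); 4,000 runs. The last column is the approximate chance that a 95% interval excludes 0.89, Φ(0.07/SE − 1.96). Prevalence is 35%.

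| AUC | RFR SD | SE of cut-off | 1.96×SE | 95% sampling range | Excludes 0.89 |
|---|---|---|---|---|---|
| 0.70 | 0.05 | 0.0213 | 0.042 | 0.775–0.855 | 0.91 |
| 0.70 | 0.08 | 0.0341 | 0.067 | 0.755–0.885 | 0.54 |
| 0.70 | 0.12 | 0.0510 | 0.100 | 0.715–0.915 | 0.28 |
| 0.80 | 0.08 | 0.0253 | 0.050 | 0.765–0.865 | 0.79 |
| 0.90 | 0.08 | 0.0187 | 0.037 | 0.785–0.855 | 0.96 |

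At AUC 0.70 and SD 0.08, the SE runs from 0.033 (50% ischaemic) to 0.039 (20%).

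**Step 3: the same check by bootstrap.** At AUC 0.70, SD 0.08 and 35% prevalence, a simulated percentile bootstrap interval excludes 0.89 in about 57% of trials if an upper limit of 0.885 or more counts as reaching 0.89 (the data are rounded to 0.01). If only 0.89 or more counts, the figure is about 70%. Under the first convention it is about 88–92% at SD 0.05, 30–38% at SD 0.12, and 91–98% at AUC 0.90 with SD 0.08, over prevalences of 20–50%. The ordering agrees with the table.

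**The case against.** The strongest reply is that the plan never undertakes to separate 0.82 from 0.89. Item 5 compares diagnostic performance, section 9.2 plans ROC analysis, and no test between the two thresholds is specified. That is correct: the 0.07 gap is a yardstick taken from the Background, not a commitment in the plan.

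Three further replies also have force.

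- The AUC of 0.70 is a design alternative, not an expected value, and a better-performing index locates its cut-off more tightly.
- The RFR standard deviation is unknown, and at 0.05 the difficulty largely disappears.
- The Youden rule is this review's assumption. A model-based midpoint would have a standard error of only about 0.008–0.011 at SD 0.08, provided its equal-variance normal model held.

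A reader might therefore be tempted to infer that 80 patients cannot tell 0.82 from 0.89. The documents do not support that. With the truth at 0.82, AUC 0.70 and SD 0.08, the sampling range of the estimate stops at about 0.885, and more favourable inputs clear 0.89 comfortably. Placing the truth between the two values, at 0.86 for example, makes most ranges cover both and so proves little. Nor is the arithmetic in 9.1 wrong, since 80 reproduces.

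These replies limit the size of the problem. None turns a test of AUC against 0.50 into a calculation of cut-off precision.

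**Conclusion.** The mismatch between the reason given for 80 and the property calculated for it stands on the text alone. Section 9.1 supports a test that the AUC exceeds 0.50, with about 89% power if about half the patients are ischaemic, about 82% at 30% and about 70% at 20%. It gives no assurance about a cut-off.

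The practical consequence is conditional. If the RFR standard deviation is about 0.08, the AUC is 0.70 and the cut-off is the empirical Youden point, its 95% range is about ±0.07 and it would often not be distinguishable from the other cited value. A larger standard deviation makes this worse; a standard deviation of 0.05 or a clearly higher AUC mostly removes it.

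This concerns a secondary objective and leaves the primary analysis untouched. It is worth correcting because the results are to be read against the earlier study. It is not a case for more patients: at SD 0.08, 1.96×SE falls only to 0.054 with 160 patients and 0.044 with 320.

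**What to change.** In section 9.1, state that 80 patients are sized to show an AUC above 0.50, give the assumed ischaemia prevalence, and remove the implication that 80 is enough to determine a cut-off. Correct the printed power.

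In section 9.2:

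- Report sensitivity and specificity with 95% confidence intervals at the cut-offs the documents already cite: 0.89 and 0.82 for the resting index, 0.80 and 0.83 for FFR. Note that 0.82 comes from iFR and is applied to RFR on the strength of their correlation.
- Name the rule for choosing any data-driven cut-off and report the cut-off with its bootstrap 95% confidence interval.
- Describe that cut-off as different from 0.82 or 0.89 only if the interval excludes the value.

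McNemar comparisons of the two cut-offs of each index, within ischaemic and non-ischaemic patients, are optional.

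The cost is a sentence or two in 9.1 and a few lines in 9.2, with no extra patients or procedures. The downside is that the claim about the cut-off becomes weaker.
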